8.5.4 Mandatory programming

Before the patient is discharged from hospital the investigator has to activate the Home Monitoring function. Furthermore capture control should be "ON" or "ATM" in all available channels (**group A**) or the RV channel only (**group B**). For both groups recording of IEGMs of episodes should be programmed to "ON".

For patients of **group A** ATP one-shot has to be programmed in the VF detection zone (see 8.5.5).

For CRT-D patients of **group A**, MPP has to be activated prior to discharge (see 8.5.6).

8.5.5 ATP one-shot programming

Prior to discharge ATP one-shot has to be programmed for patients participating in **group A** of the study. ATP one-shot has to be programmed with 8 pulses and a cycle length of 88% of the ventricular tachyarrhythmia cycle length for all patients eligible for the programming. If patients are programmed to other parameters a reason for deviation from the programming has to be provided. Furthermore, programming of Early ATP one-shot is recommended and will be documented.

8.5.6 MPP programming and measurements

In patients implanted with an HF-T QP device of the Ilivia ICD family (**group A**, CRT-D), activation of MultiPole Pacing at implantation or pre-hospital discharge is mandatory.

According to Pappone et al. 2014, in 71% of patients the highest effect of MPP is found with maximal anatomical spacing between the two stimulation vectors. Furthermore, in 57% of cases the minimum LV-LV delay was better than the longest LV-LV delay²⁶.

Thus, for programming of the feature it is recommended to choose the two vectors with maximal anatomical distance with a pacing threshold of less than 2.5 V and without phrenic nerve stimulation. For maximal anatomical distance it is recommended that pacing pulse 1 originates from LV1 ring and pacing pulse 2 originates from LV4 ring. For the LV-LV delay a programming of 0 ms is recommended. However, the programming should be adapted to the individual anatomical condition of the patient as appropriate.

During implantation, it is recommended to measure at least the pacing threshold of the recommended vectors via pacing sensing analyzer to ensure that lead placement offers adequate vector availability.

Furthermore, prior to programming, it is **mandatory** to measure all **12** available pacing vectors to determine pacing thresholds and threshold of phrenic nerve stimulation to ensure that adequate vectors are chosen. Programming has to be completed latest at pre-hospital discharge.

Figure 6 and Table 5 show the possible recommended vector combinations in regard to the anatomical distance.

[figure not shown]

Fig. 6: Recommended pacing vectors of the left ventricular lead to be used for MPP pacing

Tab. 5: Recommended vectors to be used in multipole pacing

Pacing first LV vector			Pacing second LV vector		
#	From (-) →	To (+)	#	From (-) →	To (+)
1	LV1 tip →	ICD	1	LV4 ring →	RV coil
2	LV1 tip →	RV coil	2	LV4 ring →	LV2 ring
3	LV1 tip →	LV4 ring			
4	LV1 tip →	LV2 ring			

Programming of the vectors can be freely chosen. However, if programming deviates from the recommended programming a reason for the deviation has to be documented.

For MultiPole Pacing the following information has to be documented after programming: Programmed vectors, pacing thresholds, programmed pacing amplitudes, LV sensing polarity, sensing amplitude, LV-LV delay and LV-RV delay. The physician will be asked to evaluate the usability of the MPP programming interface on the programmer.

Furthermore at each follow up, changes of the MPP programming during the course of the study have to be documented.

To determine the responsiveness of CRT-D patients to MultiPole Pacing, physicians are asked to document if a respective patient is a responder or a non-responder to CRT-D therapy at the 6-month follow-up based on his/her expert assessment of the patient status.

Furthermore, the NYHA class will be assessed and documented at implantation (values within 3 months prior to implant are acceptable) and at 6-month follow-up.

8.5.7 ICD therapy episodes and Recording episodes (event-triggered episodes)

During the course of the study IEGMs of all spontaneous occurring event-triggered medical episodes detected in both groups should be stored and forwarded to the sponsor. This includes IEGMs of non-sustained VTs, atrial episodes as well as ventricular episodes with or without ICD therapy. IEGMs based on a technical trigger do not need to be provided.

FOR-137-014-C / SOP-137-020.020 / CRQ-14-01202

For all ICD therapy episodes and ICD therapy attempt episodes in **group A** it is mandatory to provide an IEGM and evaluate the episode in the tachyarrhythmia episode form. The investigator should evaluate the appropriateness of the episode and the success of the delivered ATPs and/or shocks to terminate the episode. Furthermore physician is asked to evaluate the last 3 episodes with fast ventricular rhythm (SVT, nsVT) prior to the follow-up (if available) and enter the evaluation in the tachyarrhythmia episode form. Evaluation of atrial tachyarrhythmias is not required. However, IEGMs of all available episodes should be provided independent of the type of episode.

The Recording episodes IEGM is activated by default and has to remain activated during the course of this clinical investigation^f in both study groups (**A** and **B**). It is possible to check the activation on the Renamic programmer, by selecting the following tabs, see Figure 7:

Parameters → Diagnostics → Recording episodes → AT/AF, SVT and nsVT ON

[figure not shown]

Fig. 7: Check of activation of event triggered IEGM transmission on the programmer. A: Check of activation of all recording types; B: Check of activation of IEGM transmission via Home Monitoring

To store the IEGMs, each event has to be opened manually:

The event-triggered IEGM (Figure 8) can be displayed by selecting the button [Recordings] in the menu bar on the right.

^f Longevity of the device battery according to the Manual is calculated with recording episodes permanently set. However, it is in the investigators' decision to deactivate the function after study termination of the patient to save battery.

[figure not shown]

Fig. 8: Example of event-triggered IEGM as displayed on the programmer

8.5.8 MRI AutoDetect functionality

In case a patient of **group A** is planned to undergo an MRI scan, information on the MRI AutoDetect functionality will be collected if function is used. The physician should document the use of the test mode and further information. Furthermore a copy of all available doctors` letters or additional written information should be forwarded to the sponsor. Home Monitoring data will be used to collect further information on the MRI process in regard to the device behavior.

8.5.9 DX programming and measurements

Information on the use of the DX functionality will be collected. The atrial sensing amplitude should be measured either manually or automatically at each follow-up for **group A**. Furthermore for CRT-D devices of **group A** further CRT statistics and information on atrial burden according to device statistics will be documented.

8.5.10 Lead measurements with pacing sensing analyser (PSA)

During implantation the physician is asked to measure sensing amplitudes, pacing impedance and pacing thresholds via PSA in all available channels for patients in **group A**. For patients in **group B** only measurements of the right ventricular lead are required. For the measurement of pacing threshold a pulse width of 0.4ms is mandatory in the RV and RA channels. Furthermore shock impedance should be measured and documented, if routinely available, in both groups, **A** and **B**.

For patients in **group A** receiving a CRT-D device, measurement of different pacing vectors is highly recommended in the LV lead to determine if adequate vectors are available for programming of MPP later on (see also section 8.5 "MPP programming and Measurements").

8.5.11 Lead measurements at each follow-up

The system performance and right ventricular lead performance is evaluated at the end of the implantation procedure and **at the end** of each follow-up for both groups **A** and **B** by either manually or automatically triggered lead measurements. For this purpose the investigator performs the threshold tests, determines pacing impedance and painless shock impedance and performs P/R-wave amplitude measurements in all available channels. In the RA and RV the pulse width must be 0.4 ms, in the LV any pulse width can be chosen. For patients in **group A** measurement of all LV pacing vectors is **mandatory** prior to programming of the MPP feature, either after implantation or at time of Pre-hospital discharge. Pacing polarities of the LV

channel must be documented. For patients of **group B**, only measurement of the right channel is required (in DX leads also sensing measurements in the atrial channel).

In group A and B the appropriate sensing and pacing should be evaluated at the 3-month follow-up. In **group A** evaluation should be done in all available channel. In **group B** only the RV channel has to be assessed, for DX leads additionally also the atrial sensing. For the evaluation it is necessary to record 10 consecutive intrinsic beats and 10 consecutive pulses with markers on the IEGM, respectively. The "freeze" button needs to be pressed to store the IEGM electronically. The sensing of the lead will be assessed as "adequate" (= the device sensed the current rhythm correctly) or inadequate. In the ventricles the additional option "no intrinsic rhythm" (= patient is fully paced) is available to describe if an evaluation of sensing is not possible. In case the sensing is considered inadequate, the reason "oversensing", "undersensing", "not measurable" (= quality/content of IEGM does not allow any discrimination if senses are correct (e.g. lead dislodgement)) or "other" will be determined. The pacing of the lead will be assessed as adequate (=successful stimulation) or inadequate. In case the pacing is considered inadequate, the reason for the evaluation is required. Possible options are "non-capture" (= no evidence of depolarization after pacing), "no output" (= failure to pace: impulses are generated by the device but is not transferred to the myocardium), "not measurable" (= quality/content of IEGM does not allow any discrimination if stimulation is successful) or "other".

All measurements and tests have to be stored and provided to the sponsor.

8.5.12 Provision of programmer data and IEGMs

During the study, programmer data containing all measurements have to be provided to the sponsor for implantation and each follow-up. Furthermore programmer data should be provided also for interim visits of the patient at the study site. To ensure that all threshold measurements are available in the programmer data, it has to be ensured that for each measured vector the pacing threshold value is actually chosen and stored (see Fig 8). IEGMs have to be actively opened once to ensure storage and export. IEGMs used during follow-up to assess pacing and sensing performance of the Plexa ICD lead (group B) have to be frozen and stored to ensure availability in the programmer export.

The programmer data and IEGMs can be provided to the sponsor by the following options:

- Upload to the EDC system
- Delivery via email to [contact]
- Delivery via USB stick
- Delivery via Report Share function to the Home Monitoring Service Center (if available)

For every export it has to be ensured that data are pseudonymized. Furthermore the xml file as well as a PDF should be provided to the sponsor.

8.5.13 Plexa ICD lead handling

In **group B**, during implantation, the handling of the Plexa ICD lead will be assessed by the implanting physician. All data will be collected on the specific eCRF "Plexa lead handling".

The physician should rate the performance as "excellent", "good", "average", "fair" or "poor". The following characteristics have to be assessed:

- Tracking from deployment to target area
- Flexibility
- Pushability
- Ability to position the lead in the RV
- Ability to extend/extract the lead
- Ability to visualize the extended screw (if routinely available)
- Ability to fixate the lead tip
- Radiopacity in final position (if routinely available)

Furthermore the number of turns needed to extend the screw should be documented.

8.5.14 Home Monitoring® Data

The sponsor will collect the patient data obtained by telemetry over the period of study participation. This will include P- and R-wave sensing, pacing impedance, painless shock impedance and thresholds, periodic IEGMs and recording episodes IEGMs and further data. The observation of Home Monitoring® data by the sponsor cannot be used as an emergency system. The investigator is responsible to follow-up the patients via Home Monitoring® and during in-office follow-ups.

8.5.15 Adverse Events

During the course of the study, all adverse events will be reported to the sponsor and to local Ethics Committees, if required by local regulations (see also section 9.10.2). All adverse events will be evaluated in their relation to the investigational devices. Reporting of adverse events is required starting from the time of signature on the patient informed consent until study termination. In case serious adverse device effects (SADE) are not solved at study termination, those shall be followed up for a maximum of 4 weeks after study termination of the patient.

8.6 Replacement of subjects

During the course of the study, patients that drop out prior to any implantation attempt do not count to the total enrollment number and can be replaced as long as enrollment in the study is still ongoing. Patients who are not implanted with an investigational device and who did not come in contact with any investigational device during implantation attempt can also be replaced.

8.7 Used devices

8.7.1 Description of exposure to the investigational device

The investigational devices used in this study are Active Implantable Medical Devices (AIMD). According to the nature of implantable devices, the devices will be implanted into the patient's body and will typically remain there for the lifetime of the device, also beyond the duration of the study.

8.7.2 List of any other medical device to be used during the investigation

Group A: The following medical devices will be used for group A (Ilivia ICD family):

Device:	BIOTRONIK Ilivia/Initica/Inlexa 7 series VR-T, VR-T DX, DR-T, HF-T QP; Intica 5 series VR-T, VR-T DX, DR-T
RA-leads:	Free of choice, if applicable
RV-leads:	Free of choice, BIOTRONIK Plexa ICD lead recommended
LV-leads:	BIOTRONIK Sentus OTW QP lead, if applicable
External programming device:	Renamic only
Programmer software:	PSW1505.A (or successors) including software for Ilivia ICD family
Remote monitoring tools:	BIOTRONIK CardioMessenger® II or II-S or Smart 3G (or successors)
Remote monitoring software:	Home Monitoring Service Center (HMSC) III (or successors)

Group B: The following medical devices will be used for group B (Plexa ICD lead):

Device:	any BIOTRONIK single, dual or triple chamber ICD; BIOTRONIK Ilivia ICD family is recommended
RA-leads:	Free of choice, if applicable
RV-leads:	BIOTRONIK Plexa ICD lead
LV-leads:	Free of choice, if applicable
External programming device:	Renamic only
Programmer software:	PSW1505.A (or successors)
Remote monitoring tools:	BIOTRONIK CardioMessenger® II or II-S or Smart 3G (or successors)
Remote monitoring software:	Home Monitoring Service Center (HMSC) III (or successors)

Group A and B: The following medical devices will be used for patients enrolled in group A and B:

Device:	BIOTRONIK Ilivia/Initica/Inlexa 7 series VR-T, VR-T DX, DR-T, HF-T QP; Intica 5 series VR-T, VR-T DX, DR-T
RA-leads:	Free of choice, if applicable
RV-leads:	BIOTRONIK Plexa ICD lead
LV-leads:	BIOTRONIK Sentus OTW QP, if applicable
External programming device:	Renamic only
Programmer software:	PSW1505.A (or successors)
Remote monitoring tools:	BIOTRONIK CardioMessenger® II or II-S or Smart 3G (or successors)
Remote monitoring software:	Home Monitoring Service Center (HMSC) III (or successors)

All medical devices are used within their intended use after CE approval or respective (study) approval by regulatory institutions in countries located outside of the CE area

8.7.3 Device settings

The mandatory device settings are summarized in the following Table 6. In general, the device programming should be medically reasonable. The following settings are **mandatory** for participation in this clinical investigation:

Tab. 6: Mandatory device programming

Parameter	Device setting
Home Monitoring	On
Capture control in all channels (group A) or RV channel (group B)	On or ATM
Recording episodes IEGM	On* (default setting)
Programmer setting	
Group A:	
MultiPole Pacing (CRT-D only) ⁹	On*
ATP one shot	On*

* as described in section 8.5

8.7.4 Number of investigational devices to be used and a justification

In the BIO|MASTER.Ilivia Family / Plexa study 105 ICDs of the Ilivia family and 185 Plexa ICD leads are required to be used, which equals one Ilivia ICD device and/or one Plexa device per patient. For justification of sample size please refer to section 11.2. However, additional investigational devices may be used due to ICD device exchange during the study.

8.8 Subjects

8.8.1 Description of patient population

Only patients with respective ICD or CRT-D indication requiring ICD or CRT-D implantation according to current clinical practice and who are planned to be implanted with a ICD of the Ilivia family and/or the Plexa ICD lead according to the investigators' decision may be enrolled into the BIO|MASTER.Ilivia Family / Plexa study. Decision for implantation of the respective BIOTRONIK devices should be based on medical decisions alone and should not be influenced by the enrollment to this clinical trial.

⁹ Continuation or deactivation of the MPP feature after study termination is in the discretion of the treating physician. For battery use please refer to the manual of the Ilivia ICD family.

Group A:

Collective: Patients with an indication for ICD therapy or cardiac resynchronization therapy with defibrillator (CRT-D) according to the current clinical practice.

Total number of patients: 105, thereof

- 26 with indication for single chamber ICD (VR-T or VR-T DX device)
- 26 with indication for dual chamber ICD (DR-T device)
- 53 with indication for triple chamber (CRT) defibrillator (HF-T QP device)

Group B:

Collective: Patients with an indication for ICD therapy or cardiac resynchronization therapy with defibrillator (CRT-D) according to the current clinical practice.

Total number of patients 185

8.8.2 Inclusion criteria

All of the following inclusion criteria have to be fulfilled for enrollment of the patient to the clinical trial:

1. Standard indication for ICD or CRT-D therapy according to clinical practice
2. *De novo* implantation or upgrade/exchange^h (**group A** only) from existing ICD/CRT-Dⁱ or pacemaker implant
3. Patient is able to understand the nature of the clinical investigation and provides written informed consent
4. Patient is able and willing to complete all routine study visits at the investigational site
5. Patient accepts Home Monitoring concept
6. Age \geq 18 years

8.8.3 Exclusion criteria

The following exclusion criteria shall **not** be fulfilled for enrollment of the patient:

1. Contraindication to ICD or CRT-D therapy, respectively
2. For CRT-D patients in **group A** only: physician not willing to activate MultiPole Pacing in the patient

^h Upgrade or exchange is not available for patients in group B due to possible interference between the previous implanted RV lead and the new implanted Plexa ICD lead (e.g. potential Adverse Events in which relation cannot be distinguished between both leads)

ⁱ Exchange of CRT-D device is only possible in group A, if patient is either already implanted with BIOTRONIK Sentus OTW QP lead or replacement of the LV lead is planned.

3. Cardiac surgical procedure planned within 6 months after implantation (including also interventional procedures like ablation, valve replacement etc.). Procedures to occur during or prior to implantation are not exclusionary.
4. Expected to receive heart transplant or ventricular assist device within 6 months
5. Life expectancy less than 6 months
6. Participation in any other interventional clinical investigation^j
7. Pregnant or breast feeding at time of enrollment

8.8.4 Drop-out criteria

8.8.4.1 Mandatory drop-out according to protocol

The investigator shall exclude a patient due to the following reasons (defined as drop-out according to protocol):

- **Group A:** Patient is not implanted with a member of the Ilivia ICD family for any reason
- **Group A:** Patient in whom explantation or replacement of the Ilivia ICD is performed
- **Group B:** Patient in whom implantation of Plexa ICD lead was planned but not performed
- **Group B:** Patient in whom explantation, replacement or repositioning of the Plexa ICD lead is performed
- Patient undergoes heart transplantation or receives ventricular assist device during the course of the study.

If a patient participates in both groups, drop-out in one group does not result in drop-out of the other group, thus the patient can continue participation in the other study group.

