Patients in both groups A and B: It is recommended that patients are implanted with both investigational devices, the Ilivia ICD family **and** Plexa ICD lead, Figure 5. Such patients can belong to both study groups and should then complete all follow-ups as required by both groups. The participation in both groups instead of only in group A or in group B can be freely chosen by the investigator based on his/her medical opinion. However, the investigation should be compliant with the study protocol for group A, group B or both, respectively.

The enrollment of patients in both study groups will be stopped independently. The project management of the BIO|MASTER.Ilivia Family / Plexa study will inform all investigators in advance in written form about the stop of enrollment of patients to both groups A and B.

After 105 patients have been enrolled into group A, or 185 into group B, further patients can receive both Ilivia and Plexa implants, but can only be enrolled into the group which is still open for enrollment. These patients are not subject to CIP required procedures related to endpoints of the group into which they have not been enrolled, and if endpoints are recorded by oversight of the investigator, they will be excluded from the analysis.

Furthermore, in case a patient enrolled in both groups, is exited from one of the groups, only data for the still active group will be provided and used for analysis from that point in time on.

[figure not shown]

Fig. 5: Overlap of both study groups. Patients implanted with an ICD device of the Ilivia family and a Plexa ICD lead can belong to both groups A and B

A study duration of about 14 months enrollment plus 6 months FU = 20 months is expected in total. First Patient In (FPI) is expected for beginning of June 2016. Last Patient In can be expected for end of July 2017 (LPI), which means that the last patient will leave the study end of January 2018 (LPO, Last Patient Out).

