8.8.5 Point of enrollment and study termination

The point of enrollment is defined as the date of signature of the informed consent form by the patient. Study related procedures, documentation and collection/following of adverse events will start from this day on.

The point of study termination is defined as date of 6-month follow-up for patients with regular study termination.

For a non-regular study termination, the following rules apply:

- If none of the investigational devices could successfully be implanted, date of study termination should be the date of the last unsuccessful implantation attempt.
- In case of replacement or repositioning of the Plexa ICD lead in patients of **Group B** date of study termination should be date of revision.
- In case of withdrawal of a patient's consent, date of study termination should be the date of withdrawal of consent.
- In case of patient death, the date of study termination should be the date of the patient's death.
- If patient is lost to follow-up, date of termination should be the date of last contact of the physician to the patient.
- If patient is defined as drop-out patient for any other reason, date of study termination should be the date of latest medical information of the patient (e.g. follow-up, IEGM).

Study related procedures and documentation should end at the day of study termination. However, Serious Adverse Device Effects which are not resolved at date of study termination will be followed for up to 4 weeks after study termination of the respective patient.

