9.8 Interim Intervention: Lead / Device Revision

For all revisions, an interim intervention eCRF has to be completed. Information has to be provided on the nature of the event, the affected device and any newly implanted devices. If the ICD is repositioned or the LV lead is revised and a Sentus QP lead remains active after the revision (**group A**), lead measurements have to be performed at the end of the revision as defined in the 3-month follow-up. Furthermore in case of CRT-D, changes on MPP programming have to be documented (**group A**), if applicable.

An Adverse Event Report has to be completed for every interim intervention.

In case of any revision with invasive corrective action, the following follow-up schedule applies:

- Patients are drop-outs in case of Ilivia and/or Plexa explantation or exchange and/or Plexa repositioning after initial implantation. In case patients participate in both groups A and B, drop-out is only applicable for the respective group.
- In case of Ilivia repositioning at any time after implantation, the initial follow-up schedule remains unchanged. The data will be used for further analysis.
- In case of unsuccessful implantation of Ilivia and/or Plexa, the patient is a drop-out patient. No further follow-ups are performed. Patients participating in both groups A and B are only considered drop-out patients in the respective group.
- In case of revision of a non-investigational device at any time after implantation, the initial follow-up schedule remains unchanged. The data will be used for further analysis.

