11.10 Procedure for accounting of all data for analysis

Due to the required strict adherence to the monitoring plan, the data acquisition of all data is ensured. In certain circumstances, the following data handling requirements need to be considered:

- 1) In case of lead explant/repositioning/exchange, additional lead implantation, or ICD repositioning at any time, the data will be used for further analysis. The corresponding follow-up schedule is described in section 9.8 Interim Intervention: Lead / Device Revision.
- 2) If a patient belongs to both groups A and B, the data will be used for the analysis of groups A and for the analysis of group B.

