6.3. Termination Date

CIP chapter 8.8.5 Point of enrollment and study termination

The point of study termination is defined as date of 6-month follow-up for patients with regular study termination. For a non-regular study termination, the following rules apply:

- If none of the investigational devices could successfully be implanted, date of study termination should be the date of the last unsuccessful implantation attempt.
- In case of replacement or repositioning of the Plexa ICD lead in patients of Group B date of study termination should be date of revision.
- In case of withdrawal of a patient's consent, date of study termination should be the date of withdrawal of consent.
- In case of patient death, the date of study termination should be the date of the patient's death.
- If patient is lost to follow-up, date of termination should be the date of last contact of the physician to the patient.
- If patient is defined as drop-out patient for any other reason, date of study termination should be the date of latest medical information of the patient (e.g. follow-up, IEGM).

Ilivia Termination Date

Data file, identifier patient_display_id_full	Variable name	Variable label	Variable level	Nominal values
study_termination	end_visdate	Date of study termination	date	n.a.
study_termination	end_group_term	Was group participation in one of the groups already terminated before the overall termination date?	nominal	No Yes, group A terminated Yes, group B terminated
study_termination	end_group_term_date	Date of group specific termination	date	n.a.
data_SAR	enddate_Ilivia_SAR ²	Date of Ilivia study termination	date	n.a.

Plexa Termination Date

Data file, identifier patient_display_id_full	Variable name	Variable label	Variable level	Nominal values
data_SAR	enddate_Plexa_SAR ³	Date of Plexa study termination	date	n.a.

7. Analysis Sets

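### Repositioning a Plexa lead ends group B follow-up although the same lead stays implanted, while protocol 11.10 says the data after lead repositioning will be used; later Plexa SADEs go uncollected

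*Protocol*

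**What the plan says.** **Sections that end participation.** Protocol 8.8.4.1 lists among the mandatory group B drop-outs a "Patient in whom explantation, replacement or repositioning of the Plexa ICD lead is performed". Section 9.8 repeats this for explantation, exchange "and/or Plexa repositioning after initial implantation". Section 8.8.5 fixes the end date, and SAP 6.3 reproduces it: "In case of replacement or repositioning of the Plexa ICD lead in patients of Group B date of study termination should be date of revision".

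**What stops at that date.** Section 8.5.15 states: "Reporting of adverse events is required starting from the time of signature on the patient informed consent until study termination". Only SADEs still unresolved are followed further, for at most 4 weeks (8.5.15, 8.8.5). A patient enrolled in both groups continues in group A, but 8.1 says that after exit from one group "only data for the still active group will be provided and used for analysis from that point in time on".

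**Section that keeps the data.** Protocol 11.10 states: "In case of lead explant/repositioning/exchange, additional lead implantation, or ICD repositioning at any time, the data will be used for further analysis". It then refers to 9.8 for the follow-up schedule.

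**The other device.** Section 9.8 states: "In case of Ilivia repositioning at any time after implantation, the initial follow-up schedule remains unchanged". The data of those patients are used. No reason is given for treating the two devices differently.

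**The concern.** Section 8.8.4.1 names repositioning separately from explantation and replacement, so a repositioned Plexa lead is the same investigational lead, still implanted. Exposure continues while collection of new group B events stops. According to 7.1 the study exists to find residual risks, and according to 4.7.7 one of Plexa's design changes is a modified fixation screw. Patients who needed a repositioning are plausibly informative about that change.

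Three things are at stake:

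- The protocol gives conflicting instructions on whether post-repositioning data exist and are used.
- Plexa safety data from the revision up to month 6 are lost.
- In a narrower set of patients, the 3-month SADE-free rate and the SAP 23.7 Kaplan-Meier estimate rest on follow-up cut short by a lead problem.

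**Working it through.** **1. The plan's own figures.** Inputs for group B: null SADE-free rate 90% (8.3.1.2), assumed rate 97% (11.2), one-sided level 1.25% and power at least 90% (11.3). Let X be the number of patients with a counted SADE. The exact test passes if P(X ≤ x | n, 0.10) ≤ 0.0125.

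- n = 166: the largest passing x is 8, with P = 0.0122. Power is P(X ≤ 8 | 166, 0.03) = 0.936. From 166 upwards power stays at or above 90%.
- Enrolment: 166 / 0.90 = 184.4, rounded up to 185.
- n = 185: the largest passing x is 9 (P = 0.0088).

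The 166/185 and the stopping count of 9 (or 10) in 11.7 are therefore reproduced. The sample size is not in question. For n = 157 to 165 the limit is 7.

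**2. What happens to a repositioned Plexa patient.**

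- *The repositioning event was a counted SADE.* Under 18.11 a device-related event corrected invasively counts, and 8.3.1.2 counts patients, not events. A later SADE adds nothing, so the primary result is the same under either rule. Later events are still missing from the 6-month safety description.
- *The repositioning was not an endpoint* (securely procedure-related, external influence, twiddling or a medical AE; 8.3.1.2, 18.11). Termination by day 60 removes the patient from the primary set (SAP 23.1 and footnote 99). Termination from day 61 leaves the patient in, as SADE-free if nothing further is recorded. The Kaplan-Meier analysis (SAP 23.7) censors at revision, possibly informatively.
- *If a later SADE were recorded anyway.* SAP footnote 100 has no condition on the termination date. With the 3-month visit missing, it accepts a first Plexa SADE up to day 121. Footnote 99 restores an early-terminated patient if that SADE fell by day 60; one terminated by day 60 with a first SADE on days 61 to 121 stays outside the set. The main gap is therefore that the event is not collected, or under 8.1 not provided and used.

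**3. How many.** The documents give no repositioning count. Predecessor figures are 4/159 = 2.5% lead-related complications, all dislodgements within 3 months (5.2.5), and 8/167 = 4.8% lead-related SADEs (5.2.2). Scaled to 185:

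- 185 × 4/159 = 4.7
- 185 × 8/167 = 8.9

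This assumes that every such event leads to a repositioning, which 5.2.2 does not say. Most of these patients would belong to the first case in step 2.

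**4. Effect near the boundary.** Event counts are assumed. Take 166 evaluable patients, with k of them repositioned by day 60 for a non-endpoint reason.

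| Other SADE patients | k | Plan: k excluded | k retained |
|---|---|---|---|
| 7 | 2 | 7/164, 95.73% free, P = 0.0058, pass | both have a later SADE in the window: 9/166, 94.58%, P = 0.026, fail |
| 8 | 1 | 8/165, 95.15% free, P = 0.0129, fail | event-free: 8/166, 95.18%, P = 0.0122, pass |

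The drop-out rule favours the device in the first row and works against it in the second.

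**The case against.** **The clash with 11.10 may be only ambiguity.** Section 11.10 speaks of leads in general, includes additional lead implantation, and defers to 9.8. It could mean non-investigational leads, or data up to the revision. It says neither, however, and 9.8 uses the same phrase about further use of data for patients who stay on schedule. A site or analyst cannot tell which was meant, so the need to reconcile stands. SAP 6.3 is an excerpt of 8.8.5 and adds no independent weight.

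**Observation does not stop for everyone.** Patients in both groups, the recommended pathway in 8.1, keep their group A visits, and AE reporting runs to study termination. This is fair. The clear loss is in B-only patients. For the others, 8.1 restricts which data are provided and used, so the handling of a later Plexa SADE is unclear at best.

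**Stronger readings to avoid.**

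- A reader might infer that a later Plexa SADE can never count. Footnote 100 does not bar it.
- A reader might take 5 to 9 patients as the number biasing the primary endpoint. Most would already be endpoints, and the patients who matter need both a non-endpoint repositioning and a later SADE inside the window.
- A reader might say that the Plexa rule contradicts the Ilivia rule. A generator and a fixated lead may be handled differently; this is an unexplained asymmetry. A lead-specific reason is conceivable, since 7.1.2.2 ties month 3 to completed lead ingrowth.
- A reader might assume that repositioned patients have a higher risk of a further event. The documents give no data on this.

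**Conclusion.** The point stands in limited form. Sections 8.8.4.1, 8.8.5 and 9.8 cannot be followed together with 11.10 as worded, and new Plexa SADEs after a repositioning are lost to group B although the lead remains implanted. The certain cost is safety information up to month 6 in a residual-risk study.

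The effect on the primary endpoint is conditional on a repositioning that was not itself a counted SADE. The number of such patients cannot be derived from the documents, and the 4.7 to 8.9 range is an upper illustration for all repositionings. A change of the pass/fail result needs a count close to the limit (8 of 166, or 7 of 157 to 165) and rests on assumed events. A reader might infer that the rule systematically flatters the device; the second row of the table shows the opposite, so no direction is established. This should be corrected, but it does not undermine the design or the sample size.

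**What to change.** 1. Reconcile protocol 8.8.4.1, 8.8.5, 9.8, 11.10 and the rule in 8.1 for patients exiting one of two groups, together with SAP 6.3.
2. After a Plexa repositioning, continue AE and SADE collection through month 6, for B-only patients and for those in both groups, and use these events in the Plexa primary and Kaplan-Meier analyses. The Plexa end date then no longer falls on the revision date, so SAP footnote 99 and the censoring rule in 23.7 work without further change for these patients.
3. Flag revised patients in the sensing and pacing tables, so that a value measured after repositioning is recognisable.
4. Reword 11.10 so that it agrees with explantation and exchange remaining the end of group B participation. At present it lists those alongside repositioning.

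The cost is an amendment to wording in both documents and routine visits for a few patients. The SADE-free rate may come out slightly less favourable if later events are found.
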